We propose a randomized controlled trial comparing treatment of only affected persons presenting at our medical research center (which we will call individual treatment) to treatment of the entire household (which we will call household treatment), with both groups using the same treatment regimen with benzyl benzoate. We hereby aim to assess the practice of systematically recommending household treatment and if it provides a benefit for the index case by preventing reinfestation.

We will also assess the number of household members affected 4 weeks after treatment, by examining all household members that are present on the day of the visit. Since the presence of itching and skin lesions in a household with a diagnosed scabies case is known to be highly specific (15,17), we will also assess the number of probable scabies cases per household before and after treatment according to the judgment of the household responsible person. Cases identified this way will be defined as “probable” and cases identified through clinical diagnosis by a physician will be defined as “confirmed”.

We will further assess clinical characteristics of Scabies and demographic factors associated with its appearance in Lambaréné, Gabon, and surroundings. Although similar studies have been conducted elsewhere, little is known about Scabies in Gabon. A better understanding of the demographic profile of persons affected by the disease can benefit future control of the disease.

Study Objectives (Aims)

Primary objectives

To compare the effectiveness of individual vs household treatment for persons affected by scabies.

Secondary objectives

To compare the effectiveness of individual vs household treatment in terms of proportion of household members affected after 4 weeks.

To describe the clinical presentation of scabies and demographic profiles of persons affected presenting at our medical research center in Lambaréné, Gabon.

To assess the tolerability and safety of benzyl benzoate.

Endpoints

Primary Endpoint

The primary efficacy outcome will be clinical cure after 4 weeks.

Secondary Endpoint

Secondary endpoints will include the rate of probable and confirmed scabies cases per household after 4 weeks.

Methods and Materials

Study Population

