Study treatment and follow up

For the treatment part of this study index cases will be randomized in either of two groups and subjects of the respective household will follow the randomization outcome of the index case. Randomization will be done in RedCAP. In the first group only subjects affected by scabies shall be treated. In the second group all persons living in the same household as the index case shall be treated, and treatment will be dispensed according to the number of household members stated by the household responsible person. For both groups the choice of treatment will be a single application of benzyl benzoate 25%, which shall be mixed with an equal quantity of water for older children and with 3 parts of water for infants. Subjects will be instructed on the use of the treatment and given a standardized leaflet with instructions, however the use of the treatment will not be supervised, making this an intervention conducted in a real world setting.

Subjects will be followed up after 4 weeks. At follow up visits the subjects will be questioned about the symptoms of scabies and any adverse events experienced and examined by a physician. Cure will be defined as the clinical improvement in lesions with no new lesions. All household members present at this visit will also be examined for scabies. Subjects and household members considered not cured or newly infested will be treated.

Safety

Benzyl Benzoate is generally safe to use for all persons, including infants and pregnant women. It is contraindicated only for persons with known hypersensitivity to benzyl benzoate, which will constitute an exclusion criterium. Adverse events include skin irritation and stinging sensation(21). In case of accidental ingestion subjects are requested to contact the principal investigator.

Ethical Considerations

To maintain randomization into the individual and household treatment groups and to avoid preferential withdrawal, loss to follow up, or spillover effects the informed consent process will be performed in a two step approach.

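### Tolerability of benzyl benzoate rests on one recall question about four weeks after a single unsupervised application, so the reaction rates are likely to be unreliable.

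*Combined protocol and SAP*

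**What the plan says.** All references are to the combined protocol and SAP.

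- **Secondary objectives:** "To assess the tolerability and safety of benzyl benzoate".
- **Secondary Endpoint:** "Secondary endpoints will include the rate of probable and confirmed scabies cases per household after 4 weeks". No adverse-event endpoint is named.
- **Study treatment and follow up, exposure:** "For both groups the choice of treatment will be a single application of benzyl benzoate 25" (per cent), with "the use of the treatment will not be supervised, making this an intervention conducted in a real world setting". A standardized instruction leaflet is handed out. In the individual group only affected subjects are treated; in the household group everyone living with the index case is.
- **Study treatment and follow up, assessment:** "Subjects will be followed up after 4 weeks". Then: "At follow up visits the subjects will be questioned about the symptoms of scabies and any adverse events experienced and examined by a physician". The word for visits is plural, but only this one time point is given. Household members present at the visit are examined for scabies; the text does not mention asking them about adverse events.
- **Safety:** "Adverse events include skin irritation and stinging sensation(21" (the closing number is a literature reference). The only reporting route before week 4 is a request to contact the investigator after accidental ingestion.
- **Scabies Diagnosis and Data Collection:** a case is itching together with lesions in a typical distribution.

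**The concern.** Staff do not see the application, and the plan describes no contact between it and week 4. A local reaction at application therefore reaches the database only if the subject, or a caregiver for a young child, remembers it about four weeks later and attributes it to the product. These people were already itching, and some will still itch at the visit.

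Two errors follow. A brief sensation such as stinging may be forgotten. Skin irritation may be put down to scabies and lost, or continuing scabies itch may be reported as a reaction to the product.

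There is also a gap in who is asked. In the household group unaffected people are treated too, and a reaction is easiest to tell apart from scabies in them. Yet no adverse-event collection is described for treated household members who are not followed as subjects or who are absent that day.

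At stake is whether the trial can support a statement on tolerability. The comparison of cure between groups is not at stake.

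**Working it through.** **1. Is there a planned figure to reproduce?** None for adverse events: the plan gives no expected rate, precision or denominator. The only sample-size figure is 35 affected subjects per group, for cure of 70% versus 95%, power 80%, alpha 0.05. With a two-sided test and pooled variance (mean proportion 0.825):

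n = [1.96 × √(2 × 0.825 × 0.175) + 0.8416 × √(0.70 × 0.30 + 0.95 × 0.05)]² / 0.25² = (1.053 + 0.427)² / 0.0625 ≈ 35.06

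This rounds up to 36, and power at 35 per group is 0.799, so the stated 35 is reproduced to within one subject. It is used below only as a convenient base of 2 × 35 = 70. The number of people actually treated will differ, because the household group also treats unaffected members.

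**2. Timing of exposure and measurement.** There is one application, one follow-up at 4 weeks, no supervision, and no diary, early contact, reaction checklist, grading or attribution rule in the text. The ingestion route does not cover stinging or irritation. The week-4 question is thus the only described source.

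**3. How recall and misattribution act on the rate.** Let p be the true proportion with a reaction, r the proportion of true reactions reported at week 4, and f the proportion of people without a reaction who report one. Then

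observed rate = p × r + (1 − p) × f

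None of p, r or f is in the documents. All values below are assumptions.

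| True rate p | Recall r | f = 0 | f = 5% | f = 10% |
|---|---|---|---|---|
| 10% | 90% | 9% | 13.5% | 18% |
| 10% | 70% | 7% | 11.5% | 16% |
| 10% | 50% | 5% | 9.5% | 14% |
| 25% | 90% | 22.5% | 26.25% | 30% |
| 25% | 70% | 17.5% | 21.25% | 25% |
| 25% | 50% | 12.5% | 16.25% | 20% |
| 40% | 90% | 36% | 39% | 42% |
| 40% | 70% | 28% | 31% | 34% |
| 40% | 50% | 20% | 23% | 26% |

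**4. Reading the table.**

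- For stinging, f is plausibly near zero, because scabies as defined in the plan is itching and lesions. The f = 0 column applies and every entry is below p. With p = 25% of 70, the 17.5 expected reactions become 15.75, 12.25 or 8.75 reports at recall of 90%, 70% or 50%.
- For irritation, f may be well above zero. The errors cancel when f = p × (1 − r) / (1 − p). At p = 25% and r = 70% this is 0.25 × 0.30 / 0.75 = 10%, and the observed rate returns to 25%. With r = 90% and f = 10% it is 0.225 + 0.075 = 30%, an over-count.

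The direction is therefore probable for stinging and undetermined for irritation.

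**The case against.** The strongest reply is that adverse events are collected: subjects are questioned and a physician examines them. In a small pragmatic trial with unsupervised use, recall at the follow-up visit is a defensible choice. The objective is descriptive, both groups receive the same product, and neither the cure comparison nor the sample size depends on it. This stands, and it limits the weight of the point.

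Several stronger readings are tempting, and the documents do not support them.

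- **That the rate will be biased low.** This is too certain. Section 4 of the calculation shows that irritation can be over-counted when residual itch is reported as a reaction. The plan also gives no duration for either reaction, so brevity is an assumption, more plausible for stinging than for irritation.
- **That the question is open-ended and merged with the scabies questions.** The two topics share a sentence, but the data-collection form is not in the documents, so its format is unknown.
- **That no tolerability endpoint exists.** The list of secondary endpoints is worded as non-exhaustive. None is named for tolerability, which is as far as the text goes.
- **That those who had a bad experience and did not return could be recovered by a home record.** A record read at week 4 does not recover them.

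What remains does not depend on any of these readings: one late, memory-based collection for reactions to a single unobserved application, one of which resembles the disease.

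**Conclusion.** The concern holds in a limited form. Followed as written, the plan will give a tolerability rate that is likely to be unreliable: probably too low for stinging, and uncertain in direction for irritation. This is more than missing detail, because the timing of the only described collection is itself the source of the problem.

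The size cannot be derived from the documents. The illustrated 12.5% to 30% around a true 25% rests wholly on assumed recall (50% to 90%) and assumed false reporting (0 to 10%), and should not be read as an estimate of the error in this trial. The consequence is confined to one descriptive secondary objective, and the change is a worthwhile inexpensive improvement.

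**What to change.** Change the measurement only:

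1. At the week-4 visit, ask about stinging and about skin irritation after application by separate specific questions, recorded in their own REDCap fields apart from scabies symptoms.
2. Ask this for every treated person, including treated household members. For those absent, take the report of the person responsible for the household and mark it as such.
3. Add a short tick-box record to the leaflet for the day of application and the next few days. Read it at the week-4 visit, and use the week-4 answers where no record comes back.
4. Define the tolerability summary as the proportion of treated persons with each reaction, and report the number with no data beside it.

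The cost is a few lines on a leaflet the plan already hands out and a few data fields, with no extra visit or staff. The downsides are a small added burden on subjects, incomplete return of records, and a reported rate that may be less favourable. People in households lost to follow-up remain uncounted, which should be stated as a limitation.

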The study will be conducted at the Centre de Recherches Médicales de Lambaréné (CERMEL). Cases will be identified from patients presenting at the medical research center, which are mostly patients from screening activities conducted for malaria trials. All household members that present at the medical research center from a household with at least one case of scabies will be included. The first affected subject included of a household will be defined as the index case.

Sample size

Estimating a cure rate of 70% and 95% for individual vs. family treatment respectively we calculated a sample size of 35 affected subjects per group to provide a power of 80% with an alpha of 0,05.

When estimating that on average one additional household member affected will present at the medical research center alongside an index case, we will aim to include at least 35 different households.

Scabies Diagnosis and Data Collection

Subjects will be checked for lesions typical of scabies by a physician. The diagnosis of scabies will be made by clinical examination, a method of diagnosis which has been used in a number of other studies to diagnose scabies and has been shown to be highly sensitive and specific. Scabies will be defined as the presence of itching together with typical distribution of lesions, such as on the hands, wrists, elbows, axillae, knees, buttocks, genitalia in men, breast areolae in women, palms and soles in children under the age of two(18,19).

The lesions will be described in terms of location and spread on the body, itching and superinfection. A severity scale will be used classifying the cases into mild, moderate, severe and crusted according to the number of lesions counted. Photos of characteristic lesions and lesions of special interest will be taken. In case of lesions of unclear origin images will be assessed via a telemedical consultation by a dermatologist at the department of tropical medicine, Bernhard Nocht Institute of Tropical Medicine, Hamburg, Germany and a recommendation on treatment will be given. Images will be sent pseudonymized to protect subject privacy.

In the course of this study we will assess the use of a low-cost videomicroscope for the diagnosis of scabies, a method which has previously shown promise as a cost-effective way to definitely attribute lesions to scabies infestation(20). Thus, all patients will be examined with such a videomicroscope.

Demographic data including age, sex and household size will be assessed.

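### Household-arm drug is dispensed for members who may never have presented, but the week-4 adverse-event question is written only for subjects; a few added questions would close most of the gap

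*Combined protocol and SAP*

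**What the plan says.** Who is a subject (section Study Population): "All household members that present at the medical research center from a household with at least one case of scabies will be included". Inclusion depends on presenting.

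Who receives drug (section Study treatment and follow up): in the individual arm, "In the first group only subjects affected by scabies shall be treated". In the household arm everyone who lives with the index case is to be treated, and "treatment will be dispensed according to the number of household members stated by the household responsible person". Use is unsupervised in both arms.

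Who is asked about harm (same section): "At follow up visits the subjects will be questioned about the symptoms of scabies and any adverse events experienced and examined by a physician". The text then says "All household members present at this visit will also be examined for scabies", and after that "Subjects and household members considered not cured or newly infested will be treated". Week 4 is the only follow-up time point described.

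Other safety provisions (section Safety): the drug is contraindicated only for persons with "known hypersensitivity to benzyl benzoate, which will constitute an exclusion criterium". The one further contact route is passive: "In case of accidental ingestion subjects are requested to contact the principal investigator". Skin irritation and stinging are the adverse events named.

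The tolerability and safety of the drug is a secondary objective. No safety endpoint and no safety analysis are listed.

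**The concern.** In the individual arm, the people given drug in the first round are subjects, and subjects are asked about adverse events if they attend week 4. In the household arm, the group given drug is wider than the group asked. The difference is the household members treated without having presented, who are the people the household strategy adds. If present at week 4 they get a scabies examination and no written adverse-event question. If absent they get nothing.

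Two things are at stake, both modest. First, the safety objective would describe only part of the household-arm exposure. The missed part is unsupervised use by people whom the study staff have not seen, of a product that has to be diluted by age. Second, the protocol describes no point at which the contraindication would be checked for a member who is treated by headcount and not seen beforehand.

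**Working it through.** **The plan's own figure.** The stated size is 35 affected subjects per group, for cure rates of 70% and 95%, 80% power and alpha 0.05 (two-sided assumed). With pooled rate 0.825, the normal-approximation formula gives n = [1.960·√(2·0.825·0.175) + 0.842·√(0.70·0.30 + 0.95·0.05)]² / 0.25² = (1.053 + 0.427)² / 0.0625 ≈ 35.1, or 36 when rounded up. Power at 35 is 79.9%. The figure reproduces, and nothing below depends on it or changes it.

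**Whether subjects could mean everyone treated.** Study Population ties inclusion to presenting. In Study treatment and follow up, the sentence on week-4 treatment names subjects and household members as two groups, and the sentence before it gives household members their own, narrower procedure. All three count against the broad meaning.

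**Share of first-round household-arm exposure not asked about.** Let
- H = people living in the household,
- k = members who presented,
- u = share of non-presenters who apply the drug,
- a = share of presenters who attend week 4,

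and take every presenter in the household arm to apply the drug. Then treated = k + u(H − k), asked = a·k, and

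unasked share = [u(H − k) + (1 − a)k] / [k + u(H − k)].

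The protocol gives none of H, k, u or a. Household size is to be collected, but no figure is stated. The sample-size section expects, on average, one further affected member to present with the index case, so 2 affected presenters per household; unaffected presenters would raise k. All values below are therefore assumptions:

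| H | k | u | a | Unasked share |
|---|---|---|---|---|
| any | H | – | 1 | 0% |
| 4 | 3 | 0.5 | 1 | 0.5/3.5 = 14% |
| 4 | 2 | 1 | 1 | 2/4 = 50% |
| 4 | 2 | 1 | 0.9 | 2.2/4 = 55% |
| 8 | 2 | 1 | 1 | 6/8 = 75% |

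In the individual arm the corresponding share is 1 − a: 0% with full attendance and 10% with 90% attendance.

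The table shows how the gap depends on household size and presentation. It does not estimate the gap.

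**The case against.** The best case for the plan is that the objective is descriptive, the drug is described as generally safe, and adverse-event frequency can be reported per subject asked. Nothing in the documents suggests that non-presenters would react differently. That stands, and it keeps the point minor. It does not answer the coverage gap, because the objective is to assess the drug and the household arm gives it to people who are never asked.

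Four stronger readings are tempting, and the documents do not support them.

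- **A reader might infer that safety is compared unfairly between arms.** No between-arm safety analysis is stated, so no planned comparison is biased.
- **A reader might infer that week-4 treatment is unmonitored benzyl benzoate exposure.** The plan's cure rates imply 35·0.30 + 35·0.05 = 12.25 of 70 affected subjects not cured, if all attend, and no later contact is described. But the product given at week 4 is not named, and treatment after the endpoint can reasonably be read as end-of-study care. What remains is a scope note: solicited safety data cover the first round only.
- **A reader might infer that hypersensitivity is not checked in anyone.** For presenters, an exclusion criterion implies a check. The point is confined to members treated by headcount, and even there the leaflet and consent text are not visible and may cover it.
- **A reader might take 14% to 75% as the size of the gap.** It follows wholly from assumed values, and 0% is also possible.

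There is also a fair objection to proxy questions about absent members. They collect data on people who are not enrolled, on another person's agreement, and recall of mild irritation will be poor. Such questions should be optional.

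**Conclusion.** The point holds as a cheap improvement. As written, the plan leaves household members who were treated without presenting out of its only solicited safety contact, and describes no check of the contraindication for them before drug is dispensed. The unasked share of household-arm exposure is unknown: 0% if every member presents and attends, 50% in the example of 2 presenters in a household of 4 with full uptake and attendance.

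The conclusion rests on reading subjects as those who presented, which the protocol's own wording favours. If the sponsor means the term to include all treated household members, one sentence saying so would settle the week-4 question for members present at the visit. The primary endpoint, the sample size and the planned comparisons are unaffected.

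**What to change.** 1. **At week 4**, ask every treated household member already being examined whether the drug was applied and whether any adverse event occurred. Report adverse events per treated person asked.
2. **At the responsible person's agreement to household treatment**, ask whether any member has known hypersensitivity to benzyl benzoate, and do not dispense for that member.
3. **Optionally**, ask the responsible person the same week-4 questions about absent members, cover this in the agreement text, and report proxy answers separately. The responsible person is already to be asked about probable scabies cases before and after treatment, so the conversation exists.
4. **State the scope**: solicited safety data cover the first round of treatment only.

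The cost is a few REDCap fields and some minutes at planned contacts, with a line in the agreement text if step 3 is adopted. No visit is added. The limitation is recall: after 4 weeks mild irritation or stinging will probably be under-reported, more so by proxy. Without step 3, treated members who neither presented nor are present at week 4 remain unasked, and the report should say so.

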First all participants and/or parents/guardians (as applicable) shall be informed about all aspects of this clinical trial including the study medication. However, the respective intervention strategies (individual versus household treatment) will not be disclosed to the participants in the first step of the informed consent process. After randomization, only for the household treatment group, a person responsible for the household shall be informed about and agree to the treatment of the entire household.

The study will be conducted according to the ethical principles stated in the Declaration of Helsinki, the applicable guidelines for ICH-GCP, and the applicable laws and regulations of Gabon. Approval from the CERMEL ethics review committee will be acquired. The study will be conducted in compliance with the study protocol.

Data

Data will be collected electronically in RedCAP using the online interface and the RedCAP mobile app for offline data collection.

Funding

The trial will be institutionally funded by the Department of Clinical Research, CERMEL and the Bernhard Nocht Institute.

Bibliography

2. Fuller LC. Epidemiology of scabies. *Curr Opin Infect Dis.* 2013 Apr;26(2):123–6.
6. Burkhart CG. Scabies: An Epidemiologic Reassessment. *Ann Intern Med.* 1983 Apr 1;98(4):498.
7. Hadfield-Law L. Scratching the itch: management of scabies in A&E. *Accid Emerg Nurs.* 2000 Oct;8(4):230–2.
9. CDC - Scabies [Internet]. [cited 2018 May 22]. Available from: <https://www.cdc.gov/parasites/scabies/index.html>

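### No masked assessment of the 4-week cure verdict is described, although the two arms differ visibly and partial masking would be cheap

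*Combined protocol and SAP*

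**What the plan says.** The Endpoints section names one primary outcome: "The primary efficacy outcome will be clinical cure after 4 weeks". The section Study treatment and follow up gives its definition: "Cure will be defined as the clinical improvement in lesions with no new lesions". Both conditions must be met. No lesion count, threshold or scale is attached to improvement, and itching is not part of the definition.

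The same section describes the visit. "Subjects will be followed up after 4 weeks", and at that visit subjects are to be "questioned about the symptoms of scabies and any adverse events experienced and examined by a physician". Household members who are present are examined too. The text does not say whether one person does the questioning and the examination, or whether that person took part in randomising or dispensing.

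On allocation, "index cases will be randomized in either of two groups and subjects of the respective household will follow the randomization outcome of the index case". Affected persons are treated in one arm. In the other, treatment is supplied for everyone the responsible person reports as living in the household. RedCAP is used both for randomisation (Study treatment and follow up) and for data capture (Data).

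The only concealment is under Ethical Considerations and concerns participants: the two strategies "will not be disclosed to the participants in the first step of the informed consent process". After randomisation, the responsible person is told, in the household arm only. No section mentions masking of the physician who judges cure.

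**The concern.** The sponsor already treats knowledge of the strategy as a threat. The two-step consent is there to prevent selective withdrawal, loss to follow-up and spillover. That protection stops at the participant, while the primary endpoint rests on a physician's judgement.

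Three features together create an opening for bias:

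- **The arm is easy to learn.** The amount dispensed differs, the responsible person in one arm has been told of the strategy, and family members are seen at the same visit.
- **The judgement has room to move.** Improvement has no threshold. Finding a new lesion is more concrete, but it still depends on the examiner and on a record of where lesions were at baseline.
- **The expected direction is written down.** The Sample size section reads: "Estimating a cure rate of 70% and 95% for individual vs. family treatment respectively".

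If borderline calls lean toward that expectation, the effect estimate is inflated and the false-positive rate on the primary endpoint rises. With 35 subjects per arm, few altered calls are needed.

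**Working it through.** **Step 1: the plan's own figure.** The Sample size section states a "sample size of 35 affected subjects per group to provide a power of 80% with an alpha of 0,05". With p1 = 0.70, p2 = 0.95, mean 0.825, two-sided alpha (assumed, since sidedness is not stated) and pooled variance:

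n = [1.960 × √(2 × 0.825 × 0.175) + 0.842 × √(0.70 × 0.30 + 0.95 × 0.05)]² / 0.25²
= (1.960 × 0.5374 + 0.842 × 0.5074)² / 0.0625 = 35.06.

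Rounded up this is 36; at 35 the power is 79.9%. The stated figure reproduces, so 35 per arm is used below.

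**Step 2: a null scenario with one-sided recording error.** Inputs:

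- n = 35 per arm, from the protocol, treated as independent subjects.
- True cure p = (0.70 + 0.95)/2 = 0.825 in both arms. This is an assumption: the midpoint of the plan's two rates.
- m = share of household-arm failures recorded as cured. This is an assumption; the documents give no misclassification rate.
- Test: uncorrected two-sided chi-square at 0.05. This is an assumption; the documents name no test.

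Recorded cure in the household arm is pH = p + (1 − p) × m. The expected number of altered calls is 35 × 0.175 × m = 6.125 × m. The rejection probability is the exact sum, over all outcomes i and j from 0 to 35, of Bin(i; 35, 0.825) × Bin(j; 35, pH) wherever |z| > 1.96. Here z = [(j − i)/35] / √[q(1 − q) × 2/35] and q = (i + j)/70.

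| m | Altered calls expected | pH | False difference (points) | False-positive rate | Of which favouring household |
|---|---|---|---|---|---|
| 0 | 0 | 0.825 | 0 | 5.0% | 2.5% |
| 10% | 0.6 | 0.8425 | 1.75 | 5.5% | 3.9% |
| 20% | 1.2 | 0.860 | 3.5 | 7.0% | 6.0% |
| one third | 2.0 | 0.883 | 5.8 | 10.9% | 10.4% |
| one half | 3.1 | 0.9125 | 8.75 | 19.9% | 19.8% |

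**Step 3: sensitivity to the base rate.** With true cure of 70% in both arms, the same five values of m give 5.1%, 5.8%, 8.5%, 15.6% and 31.7%. The bias is larger because there are more failures to relabel (10.5 expected per arm instead of 6.1).

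**Step 4: can the order of the visit change without loss?** The definition of cure uses lesions only. The symptom and adverse-event questions therefore contribute nothing to the verdict, and it can be recorded before they are asked.

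**The case against.** The strongest reply is that the protocol is silent, and silence is not an admission. A reader might infer that the physician is known to see the arm, that one physician randomises, dispenses and later assesses, or that the interview always comes first. The documents support none of these as fact. They do not say who does each task or who can open the allocation in RedCAP, and the order of words in one sentence is not a visit procedure. The questions listed are about symptoms and adverse events, not about who at home was treated. All of this stands. What remains is that nothing in the text prevents the physician from knowing the arm.

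It would also be wrong to describe cure as improvement alone. The condition of no new lesions narrows the room for judgement. The protocol further describes a lesion-count severity scale and a videomicroscope for all patients, but it ties neither to the 4-week verdict.

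The error rates have no source, and the larger ones should not be read as expected. At 10% or 20% relabelling the false-positive rate is 5.5% or 7.0%, a modest rise. The calculation also treats subjects as independent, whereas the Sample size section expects about two affected persons per household.

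Finally, a reader might suppose that existing staff and forms could remove most of the bias. The documents give no staffing, rota or form design, so that share cannot be estimated.

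**Conclusion.** The point holds as a gap: no masked assessment is described for a physician-judged primary endpoint in a trial whose arms differ visibly. The documents do not show that the assessor is unmasked in practice.

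The possible size runs from negligible to serious. Under the stated assumptions the false-positive rate is 5.5% to 19.9% instead of 5.0%, and about two altered calls among 35 household-arm subjects are enough to double it. The range depends on assumed rates of relabelling in one arm only, equal true cure of 82.5%, independent subjects and an uncorrected test. The actual bias, and how much of it masking would remove, cannot be computed from the documents. The change is worth making because it is cheap and loses nothing from the endpoint.

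**What to change.** Add to Study treatment and follow up:

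1. The allocation field is hidden from the week-4 examination form in RedCAP.
2. The physician compares the subject with the baseline lesion record and enters lesion sites, lesion count, new lesions (yes/no) and the cure verdict itself. That form is saved and locked before the symptom, adverse-event and household questions are asked.
3. Where existing staffing allows, the examiner is not the physician who randomised and dispensed for that household.

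The cost is a change to form access and order, plus a rota note. Items 1 and 2 need no extra staff, item 3 applies only where staffing permits, and the sample size is unchanged.

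The limits should be stated in the protocol. Masking will be partial, because families may mention what was dispensed and the physician may remember the household. The count of probable cases reported by the responsible person is not protected. The recorded sites and counts make the verdict open to audit, but they do not by themselves set a threshold for improvement.
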